### 5.6.3 Reproductive Risks

There may be an unexpected risk to an unborn or nursing child. Pregnant and breastfeeding women will be excluded from participation in the study. Females must have a negative pregnancy test prior to enrolling in the study. Female subjects must agree not to participate in a conception process (e.g., active attempt to become pregnant or in vitro fertilization) and must agree to use a reliable and effective form of birth control (i.e., oral contraceptives, barrier methods, or abstinence) for one year after Treg dosing. Male subjects must agree to not participate in a conception process (e.g., active attempt to impregnate or sperm donation) and use birth control (i.e., oral contraceptives by female partners, barrier methods, or abstinence) for three months after Treg dosing. At every study visit the sexual activity of subjects of reproductive age will be re-assessed. If a subject who was previously sexually inactive becomes sexually active, s/he will be counseled about the need to use a reliable and effective form of birth control. Female subjects will also be required to undergo a urine pregnancy test prior to cell administration. A positive pregnancy test will result in holding of scheduled cell administration. Pregnancy tests will also be done at subsequent study visits for female subjects as described in Table 6.1, *Schedule of Events*.

Investigators of female subjects of childbearing potential on concurrent Mycophenolate Mofetil (MMF), and those subjects themselves, whether or not they plan to become pregnant, are strongly encouraged to participate in Mycophenolate Risk Evaluation and Mitigation Strategy (REMS), as described in Section 7.6.1, *Mycophenolate REMS Program*.

### 5.6.4 Malignancies

As the T lymphocytes are one major component of tumor surveillance it is theoretically possible that cells that inhibit T lymphocytes could impair this function. Therefore, the recommendations for individuals at higher risk for skin cancer apply to this research population and exposure to sunlight and UV light should be limited by wearing protective clothing and using a sunscreen with high protection factor. Refer to Section 5.7, *Concurrent Medication and Therapy*.

Subjects over the age of 50 should have age-appropriate cancer screenings at the investigator's discretion prior to enrollment and throughout the course of the study. For additional information, consult the American Cancer Society (ACS) reference below:

<http://www.cancer.org/healthy/toolsandcalculators/reminders/screening-recommendations-by-age>

#### 5.6.5 Skin Biopsies

Three 4mm skin punch biopsies from affected skin will be collected under local anesthesia for proposed mechanistic studies. In addition, APG01 will minimize discomfort and scarring by numbing a single site and performing all three 4 mm punch biopsies in a contiguous fashion, with a single resultant incision, when possible. In cases where this is not technically feasible (e.g., lesion is too small), an alternative approach is to obtain a total of three punch biopsies from two or more separate sites; when possible, punches may still be placed in contiguous fashion to minimize the total number of individual, smaller incisions. In addition to the above biopsies for mechanistic studies, a single standard 4 mm punch biopsy will be obtained during screening for subjects without prior histopathologic confirmation of their pemphigus.

In all cases, the following prioritized list of considerations will inform the investigator's clinical judgment when selecting skin biopsy sites:

1. Wound environment. Investigators will avoid repeat biopsies directly through prior biopsy scars or biopsy of any areas that appear to be potentially secondarily infected.
2. Optimal cosmesis. Preference will be given to more cosmetically favorable areas (e.g., avoid central face when possible) with favorable skin mobility to facilitate the best possible closure.
3. Abundance and size of skin lesions. Preference will be given to more numerous and larger lesions so that biopsies may be obtained from the same body region.
4. Activity of lesions. Though the activity of lesions may change throughout study duration, preference will be given to active lesions at each time point.

Skin biopsy on Week 12 may be performed on unaffected skin if no lesional skin present.

- Please note topicals should be held from the planned biopsy location for the 7 days prior to each skin biopsy. See Section 5.7, *Concurrent Medications and Therapies* and 5.8, *Prohibited Medications* for specific information on use of topical agents prior to skin biopsies.

Skin biopsy sutures should be removed per local standards.

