#### 3.4.3 Exploratory Mechanistic Endpoints

The exploratory mechanistic endpoints include the following:

- Determine the relative frequency of adoptively transferred Tregs in blood and skin by quantifying transferred deuterium-labeled Tregs in peripheral blood and skin from Week 1 to 12. In addition, TCR sequencing may be performed on sorted Tregs from either skin or blood.
- Perform whole transcriptome RNA sequencing to determine the effects of PolyTreg infusion on inflammatory and immunoregulatory pathways in the target tissue (skin)
- Quantify inflammatory cell subsets and immunologic biomarkers in blood and skin, including changes in lymphocyte subsets, cytokine profile, and autoantibody production
- Changes in disease specific and immunologic biomarkers in peripheral blood including lymphocyte subsets, cytokine profiles, polyclonal and antigen-specific Treg function (flow cytometry with MHC II-tetramer staining), and autoantibody production from baseline to Weeks 1, 2, 8, and 12

- Changes in disease specific and immunologic biomarkers in skin including lymphocyte subsets, polyclonal and antigen-specific Treg function (flow cytometry with MHC II-tetramer staining), and cytokine profiles from baseline to Weeks 1 and 12

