### 6.4 Study Procedures

- Blood donation: approximately 400 ml will be collected into a blood bag
- PolyTreg infusion: the Baseline and Day 1 visits are both a part of the 24-hour observation hospitalization for the PolyTreg infusion (see Section 5.3.2, *Administration* for details)
- Specimen collection for mechanistic studies
  - Skin biopsies: Anatomic location and disease activity will be recorded for each biopsy site

- See Section 5.6.5, *Skin Biopsies*, 5.7, *Concurrent Medications and Therapies* and 5.8, *Prohibited Medications* for information on use of topical agents prior to skin biopsies
- See Section 5.6.5, *Skin Biopsies* for the considerations to determine location of the biopsies as well as procedural steps to minimize discomfort and scarring
- See Section 6.5, *Mechanistic Assessments* for information on the studies that will be conducted on these biopsies
- Blood: Sodium heparin (green top) tubes

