### 6.5.2 Whole Transcriptome RNA-Sequencing

In order to determine if and how adoptively transferred Tregs influence diseased tissue (i.e., skin), APG01 will perform whole transcriptome RNA-sequencing of skin biopsy samples taken from lesional skin before and after Treg adoptive transfer. This will allow for a comprehensive assessment of how adoptively transferred Tregs influence gene expression in skin, with a specific focus on pathways known to be important in the pathogenesis of pemphigus. As proof of concept, UCSF has recently performed RNA-sequencing on Tregs and Teff cells isolated from normal human skin. These populations were purified from relatively small samples of skin harvested from normal healthy volunteers (Figure 14A). Initial pathway analyses in Tregs compared to Teff cells have revealed IL-27-mediated signaling to be significantly increased and the IL-23 pathway to be significantly decreased in Tregs (Figure 14B). In a similar fashion, APG01 will comprehensively compare lesional skin pre-and post-Treg transfer to elucidate the major pathways that Tregs influence in skin.

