### 8.3 Description of the Analyses

Due to the exploratory nature of this study, no confirmatory inferential analyses are planned. Descriptive statistics (such as medians, quartiles, and ranges for continuous data and percentages for categorical data) will be used to summarize patient characteristics, safety, efficacy, and mechanistic parameters. These summaries will be presented overall and separately for the subjects in the different dosing groups.

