### 8.3.3 Mechanistic Analysis

Appropriate descriptive statistics will be computed for the change in level of transferred deuterium-labeled Tregs in peripheral blood and skin from Week 1 at Week 12, changes in disease specific and immunologic biomarkers in peripheral blood and skin from baseline to Week 12, and for the relative frequency of adoptively transferred Tregs in blood and skin at each visit assessment. The mechanistic summaries will be completed using the safety population.

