**APG01 PRE-INFUSION REQUIRED CHECKLIST**

Complete this form in preparation for the PolyTreg Infusion for all subjects who have a Baseline (Day 0) visit.  
Please note that all steps listed here must be completed before the start of the infusion.

Subject ID #: \_\_\_\_\_

Baseline Mechanistic Assessments: To be obtained after eligibility has been confirmed above Answer to each item must be Yes or N/A as applicable to proceed with the PolyTreg infusion.	Yes	No	N/A
10. Three skin biopsies were obtained and processed per Protocol Section 5.5.5 and MOP Section XX .			
11. Lymphocyte subsets were drawn (3mL in lavender top EDTA tube).			
12. Mechanistic specimens were drawn (20mL in two green top sodium heparin tubes).			
Certificate of Analysis/Chain of Custody Documentation			
13. Upon receipt of the subject's Treg product for infusion from the HICTF, the Interim Certificate of Analysis and the product's Chain of Custody have been reviewed and signed.			
Comments:  
SAMPLE
			

Signature/Initials: \_\_\_\_\_ Date: \_\_\_/\_\_\_/\_\_\_

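### Unaffected skin is allowed at Week 12 only, and the skin summaries do not separate it from lesional skin, so any subject who clears mixes tissue difference with change in lesions

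*Combined protocol and SAP*

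**What the plan says.** **Tissue sampled.** Section 5.6.5 sets the default: "Three 4mm skin punch biopsies from affected skin will be collected under local anesthesia for proposed mechanistic studies". Its only exception is "Skin biopsy on Week 12 may be performed on unaffected skin if no lesional skin present". Table 6.1 schedules these biopsies at baseline, Week 1 and Week 12 (optional at unscheduled visits), and neither baseline nor Week 1 has an exception.

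**Endpoint and analysis.** Section 3.4.3 includes skin lymphocyte subsets, Treg function and "cytokine profiles from baseline to Weeks 1 and 12". Section 8.3.3 plans descriptive statistics for "changes in disease specific and immunologic biomarkers in peripheral blood and skin from baseline to Week 12", and for the Week 1 to Week 12 change in labeled Tregs in blood and skin. Section 8.3 adds: "These summaries will be presented overall and separately for the subjects in the different dosing groups". Section 8.5.3 plans no further subgroups.

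**Stated comparison.** On RNA sequencing, Section 6.5.2 says: "APG01 will comprehensively compare lesional skin pre-and post-Treg transfer to elucidate the major pathways that Tregs influence in skin".

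**Data collected.** Section 6.4 provides what a split would need: "Anatomic location and disease activity will be recorded for each biopsy site".

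**Related gating text.** Eligibility in Section 4.1 uses the PDAI overall activity score, which includes mucosal sites. Item 10 of the pre-infusion checklist (Section 15.6) asks whether "Three skin biopsies were obtained and processed per" the cited sections.

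**The concern.** The exception works in one direction only. Baseline tissue is lesional, and Week 12 tissue is lesional or, in subjects with no lesion left, unaffected. A summary that ignores this adds a difference between two kinds of skin to any change inside lesions.

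Nothing in the trial can separate the two afterwards. There is no control arm (Section 3.1.2). Baseline PDAI activity can be as low as 1, so having no lesional skin at Week 12 is plausible. Background treatment continues, and Section 5.7 allows prednisone to be raised for flares.

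What is at stake is how the skin data are read. Section 1.6.4 calls the mechanistic studies critical to understanding the biology, and Section 1.6.2 already uses skin findings from individual patients to support the choice of dose.

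**Working it through.** The plan gives no figure on this point. Its only design figure, Table 8.1, concerns safety events, but the formula carries over. 1 - (1 - p)^n at p = 0.1, 0.2, 0.3 gives 0.34, 0.59, 0.76 for n = 4 and 0.47, 0.74, 0.88 for n = 6, all as printed.

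**Inputs from the protocol**
- 4 to 6 subjects per cohort, so 8 to 12 if both cohorts run (Section 3.1).
- Tissue is affected at baseline and Week 1, and affected or unaffected at Week 12 (Section 5.6.5).
- Medians, quartiles and ranges are named for continuous data (Section 8.3).

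**Inputs not given, assumed here**
- q, the share of subjects with no lesional skin at Week 12: 0.1 to 0.5.
- D, the lesional minus unaffected marker level, in SDs of within-subject change: 1 to 3.

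**Step 1. Chance of at least one switched pair: 1 - (1 - q)^n.** At q = 0.1, 0.2, 0.3 this is 0.57, 0.83, 0.94 for n = 8 and 0.72, 0.93, 0.99 for n = 12. Within one cohort of 4 or 6 the values equal those in Table 8.1.

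**Step 2. Mean bias.** Suppose nothing changes in lesions. A lesional-to-lesional pair has expected change 0, and a switched pair has -D. The pooled mean is (1 - q) x 0 + q x (-D) = -qD.
- q = 0: 0
- q = 0.1, D = 1: -0.1 SD
- q = 0.3, D = 2: -0.6 SD
- q = 0.5, D = 3: -1.5 SD

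On a percentage scale, if unaffected skin has a fraction r of the lesional level, the mean is -share x (1 - r). With 0 of 12 switched it is 0. One of 12 at r = 0.5 gives -4.2%; 4 of 12 at r = 0.5 gives -16.7%; 6 of 12 at r = 0.25 gives -37.5%.

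**Step 3. Median bias.** This was simulated with 100,000 runs, normal change with SD 1, D = 2, and switching independent of the lesional change.

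| n | q | mean (SD) | median (SD) | median below 0 |
|---|---|---|---|---|
| 8 | 0 | 0 | 0 | 50% |
| 8 | 0.1 | -0.20 | -0.14 | 62% |
| 8 | 0.2 | -0.40 | -0.32 | 73% |
| 8 | 0.3 | -0.60 | -0.52 | 82% |
| 12 | 0.1 | -0.20 | -0.14 | 64% |
| 12 | 0.3 | -0.60 | -0.51 | 86% |

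With exactly 1 of 8 switched, the mean is -0.25 and the median -0.16.

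**Step 4. Labeled Tregs in skin.** The Week 1 to Week 12 change follows the same formula, with D now the tissue difference in labeled-Treg level. The documents do not give its sign. Section 1.6.2 hopes for trafficking to affected skin. If unaffected skin holds fewer infused cells, a switch looks like loss of cells. The cell-yield estimate in Section 6.5.1 is for affected skin only.

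**Step 5. Pairs reported separately.** In the same model, the lesional-to-lesional mean bias is 0. At q = 0.3, 0.7 x 8 = 5.6 or 0.7 x 12 = 8.4 such pairs remain; per cohort, 2.8 of 4 or 4.2 of 6.

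**Step 6. Related texts side by side.** PDAI activity runs to 250, of which 120 is mucosal (Section 15.1), so a score in the eligible range does not require skin lesions. Section 5.6.5 still asks for affected skin at Day 0 and Week 1. The checklist page with item 10 requires Yes or N/A to proceed, but item 10 shows two boxes where item 7 shows three. The explicit ineligibility rule covers items 1 to 9 only.

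**The case against.** The strongest reply is that this is a small, conditional matter. All analyses are descriptive and exploratory (Sections 8.3 and 8.5.2), so no error rate is affected. Section 8.5.5 defers detail to a later SAP. Section 6.5.2 does not name Week 12, and the Week 1 biopsy still supports the lesional comparison that it describes. The size rests wholly on assumptions. Medians also resist a few outlying values: in a noise-free case with 8 of 12 subjects at 0 and 4 at -50%, the mean is -16.7% but the median is 0.

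Most of that stands, and it limits the point. It does not remove it. Nothing commits the later SAP to separate tissue types, and with ordinary variation the median does move.

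Three stronger readings are tempting, and the documents do not support them.
- A reader might infer that the skin data will show less inflammation even if PolyTregs do nothing. That needs at least one cleared subject and a marker lower in unaffected skin, and neither is established. A subject may also have cleared because of PolyTregs, so a fall in a switched pair is not always false.
- A reader might infer that the bias always favors the product. For labeled Tregs it may run the other way.
- A reader might infer that a subject with only mucosal lesions would donate 400 ml and then be refused infusion. The checklist is ambiguous on this. The diagnostic skin biopsy in inclusion criterion 3 makes purely mucosal disease less likely, though it may date from any time before enrollment.

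**Conclusion.** The point holds in conditional form. If any subject has no lesional skin at Week 12, the pooled baseline-to-Week-12 skin summary, and the Week 1 to Week 12 labeled-Treg summary in skin, mix tissue difference with change in lesions. Inflammatory markers that are lower in unaffected skin are biased towards a fall. For labeled Tregs the direction is unknown and may be unfavorable.

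The documents do not fix the size. The figures above illustrate assumed values of q and D and are not estimates for this trial. Baseline-to-Week-1 comparisons are not affected by the exception, and neither is the primary safety endpoint. This is a cheap improvement to an exploratory analysis, not a flaw in the trial's main conclusion.

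**What to change.** **In Section 8.3.3, carried into the SAP:**
- Classify each Week 12 skin sample as lesional or unaffected from the site activity recorded under Section 6.4.
- Report lesional-to-lesional and lesional-to-unaffected pairs separately for every skin change, including labeled Tregs, and do not pool them.
- Give the number of each pair type, overall and by dose, with individual values labeled by tissue type.
- Say that lesional-to-lesional pairs leave out subjects who cleared, so that set selects on outcome and must always be shown beside the other.
- Note that this split is planned despite Section 8.5.3.

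**In Section 6.5.2:** state that Week 12 samples may include unaffected skin.

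**Cost.** No new procedure or data item is needed. The price is fewer pairs per summary; in cohorts of 4 to 6 the labeled individual values will often say more than a median.

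**Separately,** the eligibility criteria, Section 5.6.5 and checklist item 10 must be reconciled for subjects with no affected skin at Day 0 or Week 1. Item 10 also cites Section 5.5.5, whereas biopsies are in Section 5.6.5. This is a protocol and checklist clarification, not SAP wording; under Section 11.2 a protocol amendment needs IRB approval and submission to the FDA.

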#### 8.5.3 Examination of Subgroups

Due to the sample size of this phase I trial, no additional subgroup analyses will be performed.

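### Skin changes to Week 12 combine affected-to-affected with affected-to-unaffected biopsy pairs, because the analysis has no rule for biopsy-site status

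*Combined protocol and SAP*

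**What the plan says.** Section 5.6.5 sets the default site: "Three 4mm skin punch biopsies from affected skin will be collected under local anesthesia for proposed mechanistic studies". It makes one exception, for the last biopsy: "Skin biopsy on Week 12 may be performed on unaffected skin if no lesional skin present". Table 6.1 schedules these biopsies at baseline, Week 1 and Week 12, so the exception touches only the final time point.

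Section 8.3.3 promises descriptive statistics for "changes in disease specific and immunologic biomarkers in peripheral blood and skin from baseline to Week 12" and for the "change in level of transferred deuterium-labeled Tregs in peripheral blood and skin from Week 1 at Week 12". It uses the safety population and does not mention the status of the biopsied site. Section 8.3 fixes the breakdown: "These summaries will be presented overall and separately for the subjects in the different dosing groups". Section 8.5.3 adds that "no additional subgroup analyses will be performed".

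For RNA sequencing, Section 6.5.2 describes a narrower comparison: "APG01 will comprehensively compare lesional skin pre-and post-Treg transfer to elucidate the major pathways that Tregs influence in skin". Section 6.4 collects what is needed to tell the pairs apart: "Anatomic location and disease activity will be recorded for each biopsy site". No analysis section uses that information.

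**The concern.** A subject with a lesion at Week 12 contributes lesional skin before and after infusion. A subject without one may contribute lesional skin before and unaffected skin after. The second difference contains a site contrast that would exist even if nothing had changed within lesions.

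The switch is not random. It happens only in subjects whose lesions have gone, for whatever reason, so it is tied to outcome. If unaffected skin is less inflamed, the switch looks like a fall in inflammation. If unaffected skin holds fewer infused cells, the Week 1 to Week 12 change in labeled Tregs looks like poor persistence.

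At stake is the reading of the skin data. Section 3.4.3 frames the RNA-sequencing endpoint as the effect of the infusion on pathways in skin, and Section 1.6.2 relies on impact on skin inflammation when it argues for the lower dose. There is no control arm against which to calibrate a site difference. For RNA sequencing, the Week 12 exception also conflicts with the lesional before-and-after comparison in 6.5.2.

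**Working it through.** **1. The plan's own figures.** None bears on this point. The only design figure is Table 8.1, from 1 - (1 - p)^n. It reproduces: 0.344, 0.590, 0.760 for n = 4 (stated 0.34, 0.59, 0.76) and 0.469, 0.738, 0.882 for n = 6 (stated 0.47, 0.74, 0.88), at p = 0.1, 0.2, 0.3.

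**2. What each pair contrasts.**

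| Summary in 8.3.3 | Earlier site | Week 12 site, lesion present | Week 12 site, no lesion |
|---|---|---|---|
| Skin biomarkers, baseline to Week 12 | affected | affected | may be unaffected |
| Labeled Tregs in skin, Week 1 to Week 12 | affected | affected | may be unaffected |

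Section 8.3.3 does not use the word pool. The combination follows from 8.3.3 (one change), 8.3 (overall and by dose) and 8.5.3 (nothing further).

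**3. How often a cohort would contain a mixed pair.** The proportion q without lesional skin at Week 12 is not in the documents, so a range is assumed. The chance of at least one such subject is 1 - (1 - q)^n, taking every such subject to be biopsied in unaffected skin. Cohort sizes of 4 to 6 are from Table 3.1.

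| q | n = 4 | n = 6 |
|---|---|---|
| 10% | 0.34 | 0.47 |
| 20% | 0.59 | 0.74 |
| 30% | 0.76 | 0.88 |
| 50% | 0.94 | 0.98 |

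**4. Size of the shift.** Let m of n subjects switch, let D be the lesional-minus-unaffected gap, and let the true change within lesions be zero. Then

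mean change = [(n - m) × 0 + m × (-D)] / n = -(m/n) × D.

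D is not in the documents either. It is expressed here in SDs of the within-site change, with normal errors assumed. Section 8.3 names medians, so the median was simulated as well (400,000 draws per row). Without a switch, the median falls below zero 50% of the time.

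| n | m | D | Mean change | Expected median | Median below zero |
|---|---|---|---|---|---|
| 4 | 1 | 2 SD | -(1/4) × 2 = -0.50 | -0.36 | 73% |
| 4 | 2 | 2 SD | -(2/4) × 2 = -1.00 | -1.00 | 96% |
| 8 | 1 | 2 SD | -(1/8) × 2 = -0.25 | -0.16 | 65% |
| 8 | 3 | 2 SD | -(3/8) × 2 = -0.75 | -0.64 | 92% |
| 8 | 3 | 1 SD | -(3/8) × 1 = -0.38 | -0.36 | 80% |
| 12 | 1 | 2 SD | -(1/12) × 2 = -0.17 | -0.11 | 62% |
| 12 | 4 | 2 SD | -(4/12) × 2 = -0.67 | -0.55 | 92% |

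Here n = 4 is one minimum cohort, n = 8 is two of them and n = 12 is the maximum enrollment. The shift is small for one switch in a full trial and substantial for one switch in a cohort of four.

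**5. After splitting by site status.** Among affected-to-affected pairs the site-switch term is zero by construction. The price is size: n - m pairs remain, for example 3 of 4 or 5 of 8, and they exclude subjects whose lesions cleared.

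The labeled-Treg change was not simulated. The documents give no distribution of infused cells in lesional versus unaffected skin, so only the mechanism can be stated.

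**The case against.** Several points on the other side stand.

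- Section 8.3.3 is descriptive and makes no causal claim. A reader might infer that the plan reports a site difference as something PolyTregs produced. It does not. The attribution sits in the endpoint wording of 3.4.3 and in 6.5.2, so the risk is one of interpretation.
- A reader might also infer that every skin endpoint is defined on lesional skin. Only the RNA-sequencing text in 6.5.2 says so, and 8.3.3 does not name RNA sequencing. There, the fault is an inconsistency between 5.6.5 and 6.5.2. The skin biomarker endpoint in 3.4.3 refers simply to skin.
- Clearance may itself be a treatment effect, and a single-arm trial cannot separate natural course from treatment even in affected-to-affected pairs. Section 5.7 asks for stable prednisone until Week 12, which limits one alternative explanation, although increases for flares are allowed.
- Analyzing only affected-to-affected pairs would condition on a post-infusion outcome. A product that cleared lesions could then look inert.
- Section 8.5.5 promises a later SAP, which could settle the matter but is not in the documents.

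The central point survives. Followed as written, 8.3, 8.3.3 and 8.5.3 combine two different contrasts, and the switch between them depends on outcome. That is more than missing detail.

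**Conclusion.** The plan should be changed. Skin changes to Week 12 would mix affected-to-affected and affected-to-unaffected pairs, and a change in the mixture cannot be read as a change within lesions or as loss of labeled cells.

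The problem arises only if at least one subject switches. Its size is unknown. At an assumed 2 SD gap with no change within lesions, it runs from -0.17 SD (1 of 12) through -0.25 SD (1 of 8) and -0.5 SD (1 of 4) to -0.75 SD (3 of 8); it scales in proportion to the gap. The larger figures require one third or more of subjects to switch. The documents neither support nor exclude that rate. Nor do they quantify the gap in pemphigus: Section 1.3.1.5 states a lesional versus non-lesional difference in Tregs for psoriasis, and the pemphigus panel is not visible in the text reviewed.

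A reader might infer that the trial's main conclusion is at risk. The documents do not support that: the primary objective is safety and dose, and all mechanistic endpoints are exploratory.

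**What to change.** 1. Reconcile 5.6.5, 6.5.2 and 8.3.3 so that they agree on which comparison a Week 12 unaffected-skin sample may enter.
2. State in 8.3.3, with a matching exception in 8.3 and 8.5.3, that every skin summary is shown by Week 12 site status as recorded under 6.4. This includes labeled Tregs and RNA sequencing. Give counts per dose group and individual plots coded by site status.
3. Limit statements about change within lesions to affected-to-affected pairs, and say that this group is selected because subjects whose lesions cleared are not in it.
4. Report affected-to-unaffected pairs alongside, as a site contrast in subjects without lesions. They should be neither dropped nor read as within-lesion change.
5. If an overall figure is kept, label it as mixing site types.

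The cost is wording in these sections and in the promised SAP, with no extra biopsy, visit or data item. The downside is small strata and an affected-to-affected group selected on outcome. Showing both groups side by side makes that visible but does not remove it.
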